### III. PARTICIPANT SELECTION

#### A. Inclusion/Exclusion Criteria

##### **Inclusion criteria:**

- Adult patients with NYHA class I, II, or III HF admitted to an MGH inpatient unit or outpatients at the MGH Heart Center or MGH-affiliated primary care clinic. Patients with NYHA class IV HF have ongoing HF symptoms at rest, making it difficult for them to increase physical activity and other health behaviors; therefore, they will not be included. HF diagnosis will be confirmed via chart review and with the patient's treatment team as needed. NYHA class will be confirmed with the patient and adjudicated by [name] or the patient's treatment team when necessary.
- Suboptimal adherence to health behaviors. This will be defined as a total score of  $\leq 15$  on three Medical Outcomes Study Specific Adherence Scale (MOS) items regarding diet/exercise/medications. The MOS has been used in multiple prior studies assessing adherence in cardiac patients, including our own studies in this population. This threshold score on the MOS will ensure that all participants will have the potential to improve their health behaviors.

**Exclusion criteria:**

- Cognitive deficits impeding a participant's ability to provide informed consent or participate, assessed via a 6-item cognitive test that is sensitive and specific for screening for cognitive impairment in research participants.
- Medical conditions precluding interviews or likely to lead to death within 6 months.
- Inability to speak English, inability to read or write, inability to walk, or lack of a telephone.

**Justification for inclusion and exclusion criteria:** We will recruit individuals over age 18 that have NYHA class I, II, or III HF and endorse suboptimal adherence to physical activity, diet, and/or medication use. We will study HF because it is extremely common and has been associated with poor functioning and high rates of mortality (50% of individuals with HF die within 5 years of diagnosis). We chose NYHA class I, II, and III HF patients because class II and III patients comprise the majority of participants in studies that identify links between physical activity and improved exercise capacity, QoL, and survival and because class I patients also likely would benefit from increases in physical activity and health behaviors. We did not include NYHA class IV patients because they may be too physically impaired to perform some of the PP and health behavior exercises included in the intervention.

We will focus on adherence to health behaviors in HF for several reasons. First, adherence to health behaviors is associated with better HF outcomes, including lower rates of mortality, but patients with HF often struggle to adhere to these behaviors. Second, existing interventions to improve health behaviors are costly and have had limited impact on medical outcomes and QoL. Finally, positive psychological states have been associated with improved adherence to health behaviors in healthy and other medically ill populations, suggesting that an intervention to boost these states in HF patients may be an effective way to improve these behaviors and medical outcomes in general. We will enroll only those patients who have at least mild deficiencies in health behaviors.

Exclusion criteria will include cognitive deficits, medical conditions that preclude participation in the intervention or are likely to lead to death within 6 months, inability to walk, inability to speak English, and lack of a telephone. The main purpose of these exclusion criteria is to ensure that all participants are able to fully participate in intervention procedures and provide outcome data. Children under age 18 will be excluded because they often are not directly responsible for their adherence to health behaviors (e.g., medication adherence) and because they will not be able to provide informed consent. Individuals with cognitive deficits may have difficulty recalling their affective states or providing informed consent for the study. Patients who have medical impairments that lead to a high risk of dying within 6 months likely will struggle to complete the intervention and other study procedures. Potential participants without a telephone will be unable to perform the intervention and therefore will be excluded.

As physical activity (as measured by accelerometer) is our primary health behavior outcome measure, those patients who cannot walk will be excluded, as the accelerometers were primarily designed for step-based activities. Finally, individuals who do not speak or read English will be excluded because our current proposed interventional materials are only available in English and because it is unclear whether the intervention and study assessments could be effectively administered over the phone using interpreter services—certainly this would add an additional potential barrier to assessment and might result in inaccurate conclusions about the

course of illness when in fact the language barrier/interpreter presence may have been a confounding factor. If our results suggest that the intervention is promising, we will work to expand our study to non-English-speaking populations. All potential participants will be evaluated for exclusion criteria prior to enrollment, in concert with their treatment team.

## **B. Sources of participants and recruitment methods**

All participants will be adults with NYHA class I, II, or III HF admitted to an inpatient unit at MGH or seen as outpatients at the MGH Heart Center or one of MGH's primary care clinics.

**In hospital recruitment.** Potential participants will be identified through daily reviews of the inpatient unit censuses and contact with (and subsequent clearance by) an inpatient team member (physician, nurse, or nurse practitioner). If a potential participant is identified, the study staff member will ask the treatment provider to inquire whether it would be okay for a study staff member to inform the patient about an optional study. If the patient were amenable, a study staff member would meet with the patient, confirm that it is okay to describe an optional study, and then discuss the study with the patient and inquire about inclusion/exclusion criteria. Interested patients will undergo cognitive evaluation (with the six-item screen), discussion of medical history to review for exclusion criteria and confirm NYHA class, and assessment of adherence status with the MOS.

Sociodemographic and medical data (age, gender, medical and psychiatric diagnoses, NYHA class, ejection fraction, alcohol consumption, and smoking history), and baseline assessments on self-report measures (including health behaviors), will be obtained at enrollment.

**Outpatient recruitment via Research Patient Database Registry (RPDR).** All participants will be adults with NYHA class I, II, or III HF listed in their electronic medical record. Participants can be referred to the study by an outpatient treatment team member (physician, nurse, or nurse practitioner) or through systematic searches using the Partners Healthcare RPDR. The RPDR is a centralized clinical data registry that gathers data from various hospital legacy systems and stores it in one place. Researchers access this data using the RPDR online Query Tool. They may query the RPDR data for aggregate totals and, with proper IRB approval, obtain medical record data. The RPDR ensures the security of patient information by controlling and auditing the distribution of patient data within the guidelines of the IRB and with the use of several built-in, automated security measures.

To identify potentially eligible patients:

- 1.) An RPDR query will be performed to identify those patients with a diagnosis of HF. Study staff will review the medical record to confirm potential participant eligibility and to identify their linkage to a cardiologist in the MGH Heart Center or primary care physician located in an MGH primary care clinic.
- 2.) Study staff then will obtain permission for initial contact from each potentially eligible patient's cardiologist or PCP via e-mail or by having providers review letters and discard ones that they do not approve.
- 3.) For physician-approved patients, study staff will send a study introduction letter from the patient's physician (with the clinician's name at the bottom) and a study opt-out letter signed by [name] (PI). The letter from the cardiologist or PCP informs the patient that he or she is allowing the study to contact patients with HF in

case they are interested in learning about the trial. [name] letter is an opt-out letter describing the study, the procedure to opt out of further contact, and whom to call for further information. These letters will be sent from a central location at MGH.

- 4.) For patients who were contacted for the previous phase of the study and agreed to be contacted in the future, study staff will send an opt-out letter from [name] describing this new phase, the procedure to opt out of further contact, and whom to call for further information.
- 5.) Should study staff receive no reply within 10 days, staff members will call the patient on the phone to assess interest in the study and to describe the study over the phone. If the patient remains interested, staff will confirm eligibility and assess for exclusion criteria. If the patient remains interested and appears eligible, study staff will set up an appointment time to go through the consent procedures and conduct the initial study visit. We will then mail or e-mail participants a consent form to look over ahead of time, so that they may prepare questions for the first visit. Note: If a participant prefers to perform all study visits by phone, a consent form will be mailed to the participant. This will be reviewed over the phone, and if the patient remains interested, he or she will sign the consent form and mail it back to study staff at MGH. Once the signed consent form is received, study staff will mail study materials to the participant, and the participant will be called for the first study visit.

For potentially eligible patients who are enrolled in the MGH Research Options Direct to You (RODY) Program, we will send them an opt-out letter and call 10 days later to inform them about the study. RODY identifies patients who are willing to be contacted directly about research studies. Patients who have agreed to be contacted directly are identifiable through the RPDR search; each patient's RODY status is available in the demographics table included in the RPDR output.

**Future Studies.** For participants approached either inpatient or outpatient, we will inquire at the end of the screen about whether they are interested in being contacted for future studies. This will allow us to create a database for contacting patients regarding any research studies we conduct in the future. In this phase, we will be contacting potential participants who were approached for the previous phases of REACH for Health, and who were interested in being contacted in the future.

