Research suggests that PP interventions may be effective in cardiac populations. Positive affect induction, though not a formal PP exercise, has been associated with increased medication adherence and greater physical activity in hypertensive patients and in post-percutaneous coronary intervention patients, respectively. Furthermore, in a pilot trial by our group, a formal, 4-week PP intervention for cardiac inpatients was feasible, acceptable, and associated with greater numerical improvements in psychological outcomes compared to relaxation response and attentional control groups. In a second preliminary study in patients who had suffered an acute coronary syndrome (ACS), a PP intervention led to improvements in depression, anxiety, and positive affect compared to treatment as usual.

However, aside from our research group's work, no studies have evaluated formal PP interventions to promote health behaviors in cardiac patients in general or HF patients in particular. Such interventions have the potential to leverage positive psychological states to improve health behaviors in this high-risk group of patients. Further study of these interventions is critical to determine how they can be applied to HF patients.

To address this question, we recently completed qualitative interviews with 32 HF patients (IRB # 2015P000069) to better understand their HF symptoms, examine the relationships between positive psychological constructs and health behaviors, and identify barriers and facilitators to completing health behaviors. The information gained from these interviews allowed for the creation of an intervention that was adapted to this specific population. Next, we performed a single-arm, proof-of-concept trial (N=11, IRB#2016P001443) to examine the feasibility of the intervention and our outcome measures, as well as to gain preliminary feedback from participants. Based on this information, we have created an optimized, 12-week, telephone-delivered, PP-based health behavior intervention and aim to examine its feasibility, acceptability, and preliminary impact in a group of patients with mild to moderate HF in a randomized, controlled pilot trial.

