[name] also has significant experience with providing guidance and motivation towards goal-setting from the ongoing work in cardiac patients. [name] currently is the Project Director of another study examining the efficacy of PP and goal-setting interventions in patients with ACS. This study utilizes a nearly identical MI-based control condition, with which [name] has experience. Both the goal-setting portion of the PP-based intervention and MI-based control condition aim to improve health behaviors that studies have shown to be critical for cardiac health in patients with HF. Similar to his training related to the PP exercises, [name] will review the treatment manuals for this project and complete each exercise to gain experience providing education and setting goals related to physical activity, sodium restriction, and medication adherence.

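### Earlier-phase REACH patients are re-contacted and up to 11 who already received the positive psychology (PP) programme are not excluded, so feasibility may be overstated and arm contrasts diluted

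*Combined protocol and SAP*

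**What the plan says.** Section III.B of the combined protocol and SAP describes re-contact twice. Step 4 of the outpatient procedure sends an opt-out letter: "For patients who were contacted for the previous phase of the study and agreed to be contacted in the future". Step 5 follows with a telephone call if there is no reply. The Future Studies paragraph adds: "In this phase, we will be contacting potential participants who were approached for the previous phases of REACH for Health", restricted to those who had said they were interested in future contact.

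Section I.A describes the earlier phases. In one, "we recently completed qualitative interviews with 32 HF patients". In the next, "we performed a single-arm, proof-of-concept trial (N=11, IRB#2016P001443". Because that trial had a single arm, everyone in it was assigned the PP-based health behavior programme. Section I.B calls it a 10-week version, and section I.C says the present intervention is an optimized form of it.

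The exclusion criteria in III.A cover cognitive deficits, medical conditions, and: "Inability to speak English, inability to read or write, inability to walk, or lack of a telephone". Neither the criteria nor their justification mentions earlier receipt of PP, goal-setting or MI. The baseline data in V.E do not include prior exposure, and the randomization text in IV.C describes no stratification by it.

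The Training text in V.A mentions "another study examining the efficacy of PP and goal-setting interventions in patients with ACS" and adds: "This study utilizes a nearly identical MI-based control condition".

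**The concern.** Followed literally, the recruitment procedure allows someone who has already been through the preceding programme to be sent a letter, called, found eligible (with a score of 15 or less on the three adherence items) and randomized to any arm. Nothing would prevent this, and nothing in the planned baseline data would show that it had happened.

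In the PP arm the primary outcome is at stake. Feasibility is judged by whether a majority complete at least 7 of 12 sessions. People who finished a similar programme and volunteer again may well complete more readily than people offered it for the first time, which is the population of interest. Their ratings of ease, helpfulness and immediate change in mood and optimism would not be first-exposure ratings either.

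In the TAU and MI arms, prior recipients would bring PP skills into the comparison groups. That would shrink the contrasts that make up Aims 2 and 3.

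**Working it through.** **Inputs from the document.** 20 participants per group and 60 to be randomized (VI.D). Expected completion 80%, null 50%, two-sided 0.05 binomial test (VI.D). Feasible if a majority complete at least 7 of 12 sessions (V.E, VI.A and B), so at least 11 of 20. 90% of proof-of-concept participants completed the majority of exercises (VI.D). At most 11 previously treated people (I.A).

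**Assumptions.** The number re-enrolling is not documented, so it is varied. Prior recipients are given a 90% chance of completing; this carries a first-exposure rate over to a second run. Allocation is taken as equal, as 20 per group implies.

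**The plan's own figure.** The exact two-sided 0.05 rule for n=20 against 50% needs at least 15 completers: P(Bin(20, 0.5) ≥ 15) = 0.0207, doubled 0.041. Power is P(Bin(20, 0.8) ≥ 15) = 0.804. The stated power of at least 80% is reproduced. (The power text counts 5 of 8 exercises where the feasibility rule counts 7 of 12; this does not affect the arithmetic.)

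**Effect on the feasibility decision.** Let k of the 20 PP participants be prior recipients and p the completion rate in new patients. The number of completers is Bin(k, 0.9) + Bin(20−k, p).

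| k | expected completion, p=0.50 | P(≥11), p=0.50 | P(≥15), p=0.50 | P(≥11), p=0.80 |
|---|---|---|---|---|
| 0 | 50% | 0.412 | 0.021 | 0.997 |
| 1 | 52% | 0.482 | 0.030 | 0.998 |
| 2 | 54% | 0.556 | 0.042 | 0.998 |
| 3 | 56% | 0.630 | 0.058 | 0.999 |

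The expected completion is (0.9k + 0.5(20−k))/20, or 2 percentage points per prior recipient. If prior recipients were certain to complete, P(≥11) at p=0.50 would be 0.500, 0.593 and 0.685 for k=1, 2 and 3.

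**How large k could be.** If m of the 60 randomized are prior recipients, the expected number in PP is m × 20/60: 1 for m=3, 2 for m=6, 3.7 for m=11. Averaging over the hypergeometric distribution of k with m=11, at p=0.50 and 90% completion, gives P(≥11) = 0.67 and P(≥15) = 0.079. That is the ceiling for the known REACH pool under these assumptions.

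**Dilution of the contrasts.** Let a fraction f = m/60 of each arm be prior recipients, on average. Assume they retain the full PP effect D and gain nothing from repeating the programme. The PP arm then averages D and a control arm averages f × D, so the contrast is (1−f) × D. For m=3, 6 and 11, f is 3/60 = 5%, 6/60 = 10% and 11/60 = 18%.

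**The case against.** A reader might infer that feasibility is inflated as a matter of fact. The document does not support that. Prior recipients would have to re-enrol, pass the adherence screen, be allocated to PP and complete more sessions than new patients, and none of these is shown. The re-contact list also includes people who declined and the 32 interviewees, so it does not target the treated. The 90% in VI.D, and the 100% reported in I.B for the first five participants, are first-exposure rates; they suggest that new patients also complete well. A second, longer run might even lower completion. All of this stands, and it is why the direction is only probable.

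The effect on the decision is also small where the plan expects to be. At 80%, or at the 75% lower end of the team's prior work (P(≥11) = 0.986 with k=0 and 0.993 with k=3), the majority rule is met almost regardless. The effect matters only if the true rate is near 50%, which is where the rule has to discriminate.

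Randomization spreads prior exposure across arms on average, so the contrasts are diluted rather than tilted towards PP. VI.D says the trial is not designed to detect between-group differences in health behavior outcomes, and Aims 2 and 3 hypothesise only numerically greater improvement than the controls. That limits the consequence, but the contrasts will still be reported.

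A reader might also infer material contamination from the team's trial in acute coronary syndrome (ACS). Its participants are not on the re-contact list and could enter only by ordinary recruitment. Listing ACS among baseline variables says nothing about how common it is, and no overlap figure is given. That route is possible but cannot be sized.

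**Conclusion.** The gap is real: the recruitment text reaches people who had the preceding programme, and the plan does not exclude them, record their exposure or stratify by it. The supported conclusion is that feasibility and exercise ratings may be biased, probably upward, and that the PP–TAU and PP–MI contrasts may be diluted.

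The size depends on an undocumented re-enrolment number and is capped by N=11. With one to three prior recipients in PP completing at 90%, and new patients truly at 50%, the chance of meeting the majority rule rises from 41% to 48–63%, and the upper-tail error of the binomial test from 2.1% to 3.0–5.8%. At the planned 80% the majority decision is essentially unaffected. The 5%, 10% and 18% dilution figures rest on full retention of the PP effect and no gain from repetition. The point is worth correcting because it touches the primary outcome and is cheap to close; it does not undermine the design.

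**What to change.** 1. Add to III.A an exclusion for anyone who previously received any session of the REACH PP/goal-setting intervention (IRB 2016P001443), checked against the team's own enrolment logs.
2. In III.B, limit step 4 and the Future Studies re-contact to people approached but not treated. Interview-only participants and earlier decliners remain eligible.
3. Add to the baseline data in V.E any past or current participation in the team's other PP or MI trials. Recording is enough here, since the overlap is unknown.
4. If any previously treated person has already been randomized, report the feasibility proportion and the between-arm contrasts with and without them.

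The cost is at most 11 potential recruits, plus one baseline item. The planned power of 80.4% is unchanged provided 20 PP participants are still randomized.

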## **IV. PARTICIPANT ENROLLMENT**

### **A. Methods of Enrollment**

We will enroll participants through the recruitment procedures, described above, and the informed consent procedures, described below.

### **B. Procedures for obtaining informed consent**

If the patient is interested in the study after the discussion/assessment for exclusion criteria as mentioned above, a licensed physician, psychologist, social work investigator, medical student, or research assistant will verbally discuss the study in detail and give the patient

adequate time to read a written IRB-approved consent form and to ask questions. If they desire, participants will have at least 24 hours to consider enrollment. To ensure that participants have the capacity to provide informed consent, we will ask potential participants to describe their understanding of the study's purpose and their role (e.g., that they understand the timing of the intervention and its purpose, audiotaping of phone sessions and the purpose for the audiotaping, confidentiality and its limits, our focused review of medical records, and their ability to end participation in the study at any time for any reason). Patients will be given at least 24 hours if desired to consider participation in the study.

Participants also will be informed that they will receive a check for \$40 after completing the week 12 follow-up assessment in addition to wearing and returning the step counter. Participants will receive an additional check for \$60 after completing the week 24 follow-up assessment and returning a second worn step counter. Participants must return the step counter in good condition and with at least 5 days of usable data in order for remuneration to be appropriated. For tax reasons, a social security number is required in order to issue the full \$100. However, if a participant is uncomfortable giving that information, they can be compensated with a \$50 check after the completion of both follow-up assessments. Outpatient participants who come to MGH for an initial in-person visit also will be informed that they will be reimbursed for parking.

It is exceedingly unlikely that a potential participant will be a patient currently in an investigator's clinical practice. However, if an investigator discovers that a potential participant is a member of his/her clinical practice, an alternate investigator will be substituted to provide a description of the study and obtain informed consent.

Finally, once a participant signs the consent form, the investigator will perform a focused review of the participant's medical record (including laboratory data) to again confirm that the patient has HF, and will consult with the study cardiologist in the event that there is any need for further clarification. If there is a question about the patient's medical prognosis (to assess whether the patient has a condition likely to lead to death within 6 months) the study team will consult with the patient's inpatient or outpatient team and/or the study cardiologist. Participants will be asked to sign a release form at the time of consent to allow study staff to discuss their diagnosis and aforementioned medical variables during the study.

Partners Healthcare has an electronic system that lets the participants' study doctors know if they are admitted to a Partners Hospital, or if they visit a Partners Hospital Emergency Department. We will use this system to ensure that the study doctors know about any possible problems or side effects participants experience while taking part in the study.

